7 STUDY PROCEDURES

The following sections provide a detailed listing of the procedures and studies to be performed in this protocol at designated time points.

7.1 Recruitment and General Screening

Subjects may be recruited from a variety of sources including, but not limited to, subjects previously enrolled in vaccine trials at the clinical sites, the use of a center-wide IRB-approved screening protocol, and/or by the use of study-specific IRB-approved print, electronic and/or other media advertising.

A screening visit may be scheduled after an initial phone screen by clinic staff using an IRB-approved Pre-Screening Assessment form. The initial phone screen focuses on providing background information of the trial and a review of basic inclusion and exclusion criteria.

During the screening process, which may require more than one visit, the subject will read the consent form, be encouraged to ask questions, and then complete a comprehension assessment. Study staff will review and discuss the answers from the assessment to identify those areas of the informed consent form that need further review with the subject. This procedure will help ensure that the subject has sufficient understanding of the study before the consent form is signed. The subject may either sign the consent form during the screening visit or return after further consideration. The subject will have a medical history review, pregnancy prevention counseling (if female), physical exam and lab specimens drawn during the general screening process.

7.2 Screening Procedures

Subjects will undergo the following screening procedures within 60 days of inoculation:

1. Screening questions for COVID-19.
2. Explain the study and Informed Consent to the subject.
3. Ensure that the subject has successfully completed the Informed Consent comprehension assessment, has signed the Informed Consent, and receives a copy of the signed Informed Consent.
4. Within 14 days of inoculation, ensure that HIV pre-test counseling has been performed and ensure that the subject has agreed to HIV testing (required by MD state law only).
5. Elicit a complete medical history, including menstrual, sexual, and contraceptive history and history of surgical sterilization for all subjects.

6. Perform a complete physical examination, including vital signs (height, weight, blood pressure, respiratory rate, heart rate, and temperature).
7. Obtain approximately 40 mL of blood for the following laboratory screening tests:
 - Prothrombin time/partial thromboplastin time (PT/PTT)
 - Complete blood count (CBC) with differential
 - Alanine aminotransferase (ALT)
 - Aspartate aminotransferase (AST)
 - Total bilirubin
 - Previous flavivirus infection
 - Creatinine
 - Alkaline phosphatase
 - HBV
 - HCV
8. Obtain approximately 5 mL of blood for HIV testing (will be performed within 14 days of inoculation). Alternatively, a rapid HIV test may be used if a Clinical Laboratory Improvement Amendments (CLIA) waiver has been granted to the site.
9. Nasopharyngeal (NP) or mid-turbinate swab to test for SARS-CoV 2 – the virus that causes COVID-19 – will be collected from all volunteers regardless of vaccination status based on guidance from federal, state, local, and/or institutional health officials* or at the discretion of the clinician (may be collected up to 72 hours in advance of stated collection time).

*This guidance may be informed by the local COVID infection rate, severity of infections, vaccination rates, and other factors as the COVID-19 pandemic continues to evolve and change.

10. Obtain urine for urinalysis by dipstick testing (glucose, bilirubin, ketones, specific gravity, blood, pH, protein, urobilinogen, nitrite, leukocyte esterase).
11. Obtain serum for β -HCG testing in females. A positive β -HCG will exclude the subject from the trial. Obtain FSH for females who have not menstruated for greater than 12 months but less than 24 months.
12. If necessary, obtain medical release form to confirm method of birth control.
13. Counsel all female subjects to avoid becoming pregnant during the study and on pregnancy prevention during the entire study period.
14. Counsel all male subjects to use barrier contraception for the three months following vaccination.

7.3 Inoculation Procedure

Subjects will receive the LA Zika vaccine rZIKV/D4Δ30-713 or placebo on Study Day 0. The vaccine will be kept frozen at $-75^{\circ}\text{C} \pm 15^{\circ}\text{C}$ until just before use, whereupon it will be thawed, diluted to the appropriate dose, and drawn up for administration (see Section 6 for test article preparation). The rZIKV/D4Δ30-713 vaccine will be kept on wet ice from the time it is thawed until it is diluted with PlasmaLyte into its final formulation. The vaccine and placebo (PlasmaLyte) will then be delivered at room temperature or on wet ice to clinical staff for administration. A volume of 0.5 mL of test article will be delivered by subcutaneous injection in the deltoid region of the upper arm with a needle of appropriate gauge and length after wiping the injection site with alcohol.

7.4 Detailed Study Procedures

The study procedures to be performed at each visit are listed below. Additional tests may be done at the discretion of the PI/provider to evaluate concomitant illness or further evaluate an adverse event (AE) experienced by a subject. Photographs may be taken of the injection site. In addition, photographs may be taken of other areas of the skin before and/or after inoculation to record the characteristics of any rash that may develop. Possible identifiers, such as tattoos, jewelry, and clothing will not be included in the photographs, to maintain confidentiality. The total volume of blood to be drawn over the 26-week post-vaccination period is approximately 610 mL. This amount is within NIH guidelines (Medical Administrative Policy 95-9) for adult blood donation and should not compromise the health of study subjects. A topical anesthetic cream may be used during blood draw at the phlebotomist's discretion to ease the discomfort of the procedure.

7.4.1 Inoculation and Follow-up

On the day of inoculation with test article, more subjects may be invited to the clinic than will be enrolled. These subjects will be alternates and will be inoculated only if other subjects are not available for inoculation or are found to be ineligible on the day of inoculation. Those subjects who are alternates will be informed that they are alternates when they are invited to the clinic. For study visits with overlapping windows for the visit, subjects will be scheduled so that 2 study visits for an individual do NOT occur on the same day. All subjects invited to the clinic will have to abide by the facility's masking policies and COVID-19 related procedures. At each visit, volunteers will be asked whether or not they have experienced any COVID-19 symptoms (per facility screening guidelines) or if they have had an exposure to someone with COVID-19 prior to coming into the clinic. If the volunteer reports symptoms consistent with COVID-19 and they are already enrolled in the study, an NP or mid-turbinate swab will be collected and tested for COVID-19 on site or at the respective local laboratory. If this is unavailable, the volunteer will be referred for local testing. The volunteer will not come into the clinic until the result is confirmed to be negative (~45 minutes) or per current facility guidelines for COVID-19 screening procedures. Should a volunteer test positive for SARS-CoV-2 at any point during the study, the volunteer will be asked to quarantine according to current CDC guidelines. We will review current CDC guidelines with the volunteer. We will defer all in-person visits until after the volunteer has completed their quarantine or if a COVID-19 positive research space is available they will be brought to that location. If they test positive for SARS-CoV-2 during the first 21-days post-vaccination, scheduled follow-up visits will be done as telehealth visits or at a research space designated for COVID-19 positive patients. Based on COVID-19 testing and

results availability, NP or mid-turbinate swab may be collected up 72 hours prior to scheduled testing visit.

Study Day 0 (Day of Inoculation with Test Article)

1. Screening questions for COVID-19.
2. Verify that Informed Consent was obtained and that the consent form was signed by both the subject and by the study staff.
3. Verify that all applicable eligibility criteria have been met.
4. Perform interim history, including sexual history, and focused physical exam, concentrating on any acute complaints. Focused physical exam will include BP, HR, temperature, respiratory rate, skin examination, eyes, throat, muscle strength, and biceps and patellar deep tendon reflexes. Physical exam may extend beyond these if indicated by complaint or physical finding.
5. Review and document concomitant medications.
6. Nasopharyngeal (NP) or mid-turbinate swab to test for SARS-CoV 2 – the virus that causes COVID-19 – will be collected based on guidance from federal, state, local, and/or institutional health officials* or at the discretion of the clinician (*may be obtained up to 72 hours in advance of study day*).

*This guidance may be informed by the local COVID infection rate, severity of infections, vaccination rates, and other factors as the COVID-19 pandemic continues to evolve and change.

7. Obtain approximately 70 mL of blood for CBC with differential, ALT, creatinine, virus isolation and culture (PCR/culture), and immunology (PBMCs, plasma, and PAXGene). These laboratory studies are drawn as baseline values and will not determine eligibility.
8. Obtain 5 mL of clean-catch urine for virus isolation & culture.
9. Obtain vaginal secretion sample (women) for virus isolation and culture (may be collected at home by the volunteer).
10. Obtain semen sample (men) for virus isolation and culture (may be collected at home by the volunteer).
11. Obtain oral fluid for serology (CIR site only).
12. Perform serum or urine β -HCG testing for female subjects. Ensure the test is negative before proceeding; a positive test will exclude the subject from the study as per protocol, Section 5.2.
13. Review pregnancy prevention.
14. Record vital signs (blood pressure, temperature, heart rate, and respiratory rate).
15. Administer the test article.
16. Observe for at least 30 minutes after inoculation and evaluate for immediate hypersensitivity.

17. Provide education by study staff describing proper use of thermometer, the signs and symptoms of potential AEs, and how and when to contact study staff (see Section 7.5.1).

Study Day 4 (± 1 day)

1. Screening questions for COVID-19.
2. Perform interim history and focused physical exam, concentrating on any acute complaints.
3. Record vital signs.
4. Obtain approximately 40 mL of blood for CBC with differential, virology, and immunology (PBMCs, plasma, and PAXGene).
5. Obtain 5 mL of clean-catch urine for virus isolation & culture.
6. Review pregnancy prevention.

Study Day 6 (± 1 day)

1. Screening questions for COVID-19.
2. Perform interim history and focused physical exam, concentrating on any acute complaints.
3. Record vital signs.
4. Obtain approximately 20 mL of blood for CBC with differential, ALT, virology, and PAXGene.
5. Obtain 5 mL of clean-catch urine for virus isolation & culture.
6. Review pregnancy prevention.

Study Day 8 (± 1 day)

1. Screening questions for COVID-19.
2. Perform interim history and focused physical exam, concentrating on any acute complaints.
3. Record vital signs.
4. Nasopharyngeal (NP) or mid-turbinate swab to test for SARS-CoV 2 – the virus that causes COVID-19 – will be collected based on guidance from federal, state, local, and/or institutional health officials* or at the discretion of the clinician (*may be obtained up to 72 hours in advance of study day*).
5. Obtain approximately 50 mL of blood for CBC with differential, virology, and immunology (PBMCs, plasma, and PAXGene).
6. Obtain urine sample for virus isolation and culture.
7. Obtain vaginal secretion sample (women) for virus isolation and culture. Vaginal cup may be inserted at home by the volunteer prior to presentation to the clinic.
8. Obtain semen sample (men) for virus isolation and culture, may be collected at home by the volunteer prior to presentation to the clinic.
9. Obtain oral fluid for serology (CIR subjects only).
10. Review pregnancy prevention.

*This guidance may be informed by the local COVID infection rate, severity of infections, vaccination rates, and other factors as the COVID-19 pandemic continues to evolve and change.

Study Day 10 (± 1 day)

1. Screening questions for COVID-19.
2. Perform interim history and focused physical exam, concentrating on any acute complaints.
3. Record vital signs.
4. Obtain approximately 20 mL of blood for CBC with differential, virology, and PAXGene.
5. Obtain 5 mL of clean-catch urine for virus isolation & culture.
6. Review pregnancy prevention.

Study Day 12 (± 1 day)

1. Screening questions for COVID-19.
2. Perform interim history and focused physical exam, concentrating on any acute complaints.
3. Record vital signs.
4. Obtain approximately 20 mL of blood for CBC with differential, virology, and PAXGene.
5. Obtain urine sample for virus isolation and culture.
6. Obtain oral fluid for serology (CIR subjects only).
7. Review pregnancy prevention.

Study Day 14 (± 1 day)

1. Screening questions for COVID-19.
2. Perform interim history and focused physical exam, concentrating on any acute complaints.
3. Record vital signs.
4. Review pregnancy prevention with the subject.
5. Nasopharyngeal (NP) or mid-turbinate swab to test for SARS-CoV 2 – the virus that causes COVID-19 – will be collected based on guidance from federal, state, local, and/or institutional health officials* or at the discretion of the clinician (*may be obtained up to 72 hours in advance of study day*).

*This guidance may be informed by the local COVID infection rate, severity of infections, vaccination rates, and other factors as the COVID-19 pandemic continues to evolve and change.

6. Obtain approximately 50 mL of blood for CBC with differential, ALT, creatinine, virology, and immunology (PBMCs, plasma, and PAXGene).
7. Obtain 5 mL of clean-catch urine for virus isolation & culture.

Study Day 16 (± 1 day)

1. Screening questions for COVID-19.
2. Perform interim history and focused physical exam, concentrating on any acute complaints.
3. Record vital signs.
4. Obtain approximately 20 mL of blood for CBC with differential, virology, and PAXGene.
5. Obtain urine sample for virus isolation and culture.
6. Obtain vaginal secretion sample (women) for virus isolation and culture. Vaginal cup may be inserted at home by the volunteer prior to presentation to the clinic.
7. Obtain semen sample (men) for virus isolation and culture, which may be collected at home by the volunteer prior to presentation to the clinic.
8. Obtain oral fluid for serology (CIR subjects only).
9. Review pregnancy prevention.

Study Day 21 (± 1 day)

1. Screening questions for COVID-19.
2. Perform interim history and focused physical exam, concentrating on any acute complaints.
3. Record vital signs.
4. Review pregnancy prevention with the subject.
5. Obtain approximately 40 mL of blood for immunology (PBMCs, serum, plasma, PAXGene), and virology*. CBC and/or ALT or creatinine will be done if prior white blood cell (WBC), ANC, platelet count, hemoglobin, or ALT or creatinine results are Grade I or above and unresolved, as defined by protocol.
6. For females, perform β -HCG testing. A positive test will exclude the subject from the per-protocol analysis, as per Section 5.
7. Obtain urine sample for virus isolation and culture.*

*Virology will be done on Study Day 21 only if virus was recovered from the sample drawn at the previous time-point (Day 16)

Study Day 28 (± 2 days)

1. Screening questions for COVID-19.
2. Perform interim history and focused physical exam, concentrating on any acute complaints.
3. Record vital signs.
4. Obtain approximately 50 mL of blood for immunology (PBMCs, serum, plasma, PAXGene and virology*).
5. For females, perform β -HCG testing. A positive test will exclude the subject from the per-protocol analysis, as per Section 5.
6. Review pregnancy prevention with the subject.
7. Obtain urine sample for virus isolation and culture.*
8. Obtain vaginal secretion sample (women) for virus isolation and culture.* Vaginal cup may be inserted at home by the volunteer prior to presentation to the clinic.

9. Obtain semen sample (men) for virus isolation and culture, which may be collected at home by the volunteer prior to presentation to the clinic.*
10. Obtain oral fluid for serology (CIR site only).

* Virology will be done on Study Day 28 only if virus was recovered from the sample drawn at the previous time-point (Day 21)

Study Day 56 (+ 14 days)

1. Screening questions for COVID-19.
2. Perform interim history for interim complaints (physical exam is optional – will be done should subject have any medically-attended AEs since last visit).
3. Record vital signs.
4. Obtain approximately 50 mL of blood for virology* and immunology (PBMCs, serum, and plasma).
5. For females, perform β-HCG testing.
6. Review pregnancy prevention with the subject.
7. Obtain urine sample for virus isolation and culture.*
8. Obtain vaginal secretion sample (women) for virus isolation and culture.* Vaginal cup may be inserted at home by the volunteer prior to presentation to the clinic.
9. Obtain semen sample (men) for virus isolation and culture, which may be collected at home by the volunteer prior to presentation to the clinic.*
10. Obtain oral fluid for serology (CIR site only).

*Virology will be done on Study Day 56 only if virus was recovered from the sample collected at the previous time-point (Day 28).

Study Day 90 (+ 10 days)

1. Screening questions for COVID-19.
2. Perform interim history for interim complaints (physical exam is optional - will be done should subject have any medically-attended AEs since last visit).
3. Record vital signs.
4. Obtain approximately 40 mL of blood for virology* and immunology (PBMCs, serum, and plasma).
5. For females, perform β-HCG testing.
6. Review pregnancy prevention with the subject.
7. Obtain urine sample for virus isolation and culture.*
8. Obtain vaginal secretion sample (women) for virus isolation and culture. Vaginal cup may be inserted at home by the volunteer prior to presentation to the clinic.*
9. Obtain semen sample (men) for virus isolation and culture, which may be collected at home by the volunteer prior to presentation to the clinic.*
10. Obtain oral fluid for serology (CIR site only).

*Virology will be done on Study Day 90 only if virus was recovered from the sample collected at the previous time-point (Day 56).

Study Day 150 (+ 14 days)

1. Screening questions for COVID-19.
2. Perform interim history for interim complaints (physical exam is optional- will be done should subject have any medically-attended AEs since last visit or at the discretion of the investigator).
3. Record vital signs.
4. Obtain approximately 50 mL of blood for virology* and immunology (PBMCs, serum, and plasma).
5. For females, perform β -HCG testing.
6. Review pregnancy prevention with the subject.
7. Obtain urine sample for virus isolation and culture.*
8. Obtain vaginal secretion sample (women) for virus isolation and culture. Vaginal cup may be inserted at home by the volunteer prior to presentation to the clinic.*
9. Obtain semen sample (men) for virus isolation and culture, may be collected at home by the volunteer prior to presentation to the clinic.*
10. Obtain oral fluid for serology (CIR site only).

*Collection of urine, vaginal secretion, and semen samples and virology (urine, vaginal secretion, semen, blood) will be done on Study Day 150 only if virus was recovered from the sample collected at the previous time-point (Day 90) or if virology results are not available.

Study Day 180 (+ 28 / - 14 days)

1. Screening questions for COVID-19.
2. Perform interim history for interim complaints and focused physical exam, concentrating on any acute complaints.
3. Record vital signs.
4. Obtain approximately 50 mL of blood for immunology (PBMCs, serum, and plasma).
5. For females, perform β -HCG testing.
6. Obtain urine sample for virus isolation and culture.*
7. Obtain vaginal secretion sample (women) for virus isolation and culture. Vaginal cup may be inserted at home by the volunteer prior to presentation to the clinic.*
8. Obtain semen sample (men) for virus isolation and culture, may be collected at home by the volunteer prior to presentation to the clinic. *
9. Obtain oral fluid for serology (CIR site only).

*Collection of urine, vaginal secretion, and semen samples and virology (urine, vaginal secretion, semen) will be done on Study Day 180 only if virus was recovered from the sample collected at the previous time-point (Day 150) or if virology results are not available.

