3.2 Secondary Objectives

- 1) Assess the frequency, quantity, and duration of viremia after a single dose of rZIKV/D4Δ30-713 given at either 10^3 PFU or 10^4 PFU.
- 2) Evaluate the number of vaccine recipients infected with rZIKV/D4Δ30-713 given at either 10^3 PFU or 10^4 PFU. Infection is defined as recovery of infectious vaccine virus from the blood, serum, or urine of a subject and/or by seroconversion to ZIKV (plaque-reduction neutralization titer [PRNT₅₀] $\geq 1:10$) within the 90-day period following vaccination.
- 3) Evaluate the immunogenicity of rZIKV/D4Δ30-713 in flavivirus-naïve subjects as assessed by the PRNT₅₀ to ZIKV, for each subject at Study Day 28, 56, and 90 post-administration of LA Zika vaccine.
- 4) Determine the durability of antibody response 26 weeks after vaccination.
- 5) Determine the quantity and duration of ZIKV presence as determined by:
 - The peak virus titer in the blood and the duration of viremia induced by the LA Zika vaccine as determined by RT-PCR and virus culture
 - The quantity and duration of possible Zika vaccine shedding in urine determined by RT-PCR and virus culture
 - The quantity and duration of possible Zika vaccine shedding in vaginal secretions determined by RT-PCR and virus culture
 - The quantity and duration of possible Zika vaccine shedding in semen determined by RT-PCR and virus culture

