14.4 Appendix 4: Schedule of Procedures Post-inoculation with ZIKV Vaccine

Procedure	Screen	Study Day													
		0	4	6	8	10	12	14	16	21	28	56	90	150	
Informed Consent	X														
Alk.Phos, bilirubin, AST	X														
PT/PTT	X														
Urinalysis	X														
HIV test	X														
HCV test	X														
HBV test	X														
Flavivirus antibody	X														
SARS-CoV-2 PCR (NP or mid-turbinete swab)	X ⁷	X ⁷			X ⁷			X ⁷							
Physical examination	X	X	X	X	X	X	X	X	X	X	X	[X] ¹	[X] ¹	[X] ¹	X
Vital signs	X	X	X	X	X	X	X	X	X	X	X	X	X	X	X
Inoculation		X													
CBC with differential	X	X	X	X	X	X	X	X	X	[X] ⁴					
ALT / Creatinine	X	X		X ⁶				X		[X] ⁴					
Pregnancy Test	X	X								X	X	X	X	X	X
Serology (blood)		X								X	X	X	X	X	X
PBMC collection		X	X		X		X		X	X	X	X	X	X	X
PAXGene collection		X	X	X	X	X	X	X	X	X	X				
Urine for virus isolation		X	X	X	X	X	X	X	[X] ²	[X] ²	[X] ²	[X] ²	[X] ³	[X] ³	
Blood for virus isolation		X	X	X	X	X	X	X	[X] ²						
Vaginal secretion for virus isolation		X			X				X		[X] ²	[X] ²	[X] ²	[X] ³	[X] ³
Semen for virus isolation		X			X				X		[X] ²	[X] ²	[X] ²	[X] ³	[X] ³
Oral fluid for serology ⁵		X			X		X		X		X	X	X	X	X

1. [X]¹ indicates that the physical exam is optional and will be performed if the subject has had a medically attended adverse event since the last visit or at the discretion of the investigator

2. [X]² indicates that samples will be collected. Viral culture and PCR is optional and will be done only if virus was recovered from the sample drawn at the previous time-point

3. [X]³ indicates that samples for virology will be collected on study day if virus was recovered from the sample drawn at the previous time-point or virology results are not available

4. [X]⁴ indicates that the lab is optional and will be done if the previous sample was a grade 1 or higher

5. This will only be done at JHU CIR

6. ALT testing only

7. Nasopharyngeal (NP) or mid-turbinete swab to test for SARS-CoV 2 – the virus that causes COVID-19 – will be collected from all volunteers regardless of vaccination status based on guidance from federal, state, local, and/or institutional health officials* or at the discretion of the clinician (may be collected up to 72 hours in advance of stated collection time).

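### Semen and vaginal testing on Day 28 depends on a Day 21 sample not scheduled for those fluids, so testing on Days 28 to 90 may never be triggered

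*Combined protocol and SAP*

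**What the plan says.** Section 7.4.1 sets the collection and testing rules visit by visit.

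- **Days 0, 8 and 16.** Semen and vaginal secretions are collected for virology with no condition attached.
- **Day 21.** Seven items are listed. The virology specimens are blood ("Obtain approximately 40 mL of blood for immunology (PBMCs, serum, plasma, PAXGene), and virology") and urine. Neither semen nor vaginal secretions appear. The footnote reads: "Virology will be done on Study Day 21 only if virus was recovered from the sample drawn at the previous time-point (Day 16".
- **Day 28.** The list includes "Obtain vaginal secretion sample (women) for virus isolation and culture" and "Obtain semen sample (men) for virus isolation and culture, which may be collected at home by the volunteer". Both items carry the asterisk for the footnote: "Virology will be done on Study Day 28 only if virus was recovered from the sample drawn at the previous time-point (Day 21".
- **Day 56.** "Virology will be done on Study Day 56 only if virus was recovered from the sample collected at the previous time-point (Day 28". Day 90 has the same rule, pointing back to Day 56.
- **Days 150 and 180.** Genital specimens are collected and tested if the preceding time point was positive or, as a second route, if earlier virology results are lacking.

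In Appendix 4, the semen and vaginal rows have entries on Days 0, 8, 16, 28, 56, 90, 150 and 180, and none on Day 21. Note 2, which governs Days 28, 56 and 90, has the specimens collected in every case and then says: "Viral culture and PCR is optional and will be done only if virus was recovered from the sample drawn at the previous time-point". It names no day.

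Secondary Objective 5 in Section 3.2 includes "The quantity and duration of possible Zika vaccine shedding in semen determined by RT-PCR and virus culture", with a matching item for vaginal secretions.

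**The concern.** The Day 28 condition refers to a specimen that does not exist for two of the four fluids it governs. A laboratory following the footnote as written would have no Day 21 semen or vaginal result to consult. It would either leave the Day 28 specimen untested or substitute the Day 21 blood or urine result. Because Days 56 and 90 each depend on the visit before, a missing Day 28 test carries forward to both.

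The subject affected is the one the objective is about: someone with vaccine virus in semen or vaginal secretions on Day 16, for whom the question is how long it lasts. Detection in either fluid also halts enrolment under Section 8.5.1.2. That section sends follow-up of enrolled subjects back to the protocol's specimen schedule, so the DSMB and FDA could be weighing resumption (Section 8.5.3) without Day 28 to 90 results.

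**Working it through.** The plan states no figure to reproduce, and the point does not depend on sample size or error rates. The check is to follow the trigger chain.

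**Inputs.** Genital collection days are 0, 8, 16, 28, 56, 90, 150 and 180 (Section 7.4.1 and Appendix 4). In the body text the triggers are: Day 28 looks to Day 21, Day 56 to Day 28, Day 90 to Day 56, Day 150 to Day 90, and Day 180 to Day 150. The last two also have the missing-results route.

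**Test case.** A man has virus in semen at every post-dose visit, with blood and urine negative throughout. The last column assumes that specimens deliberately left untested count as missing results, which the plan does not say.

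| Reading of the Day 28 trigger | Days semen is tested | Days tested if the missing-results route applies |
|---|---|---|
| A. Body text, same fluid, Day 21 | 0, 8, 16 | 0, 8, 16, 150, 180 |
| B. Body text, any fluid on Day 21 | 0, 8, 16 | 0, 8, 16, 150, 180 |
| C. Appendix 4 note 2, previous sample of that fluid | 0, 8, 16, 28, 56, 90, 150, 180 | the same |

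Under B the result changes if blood or urine is positive on Day 21: the same man is then tested on every day from 28 to 180. Whether his semen is followed therefore depends on a different fluid, although Section 3.2 lists the fluids as separate shedding outcomes.

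**Size.** There are seven post-dose genital time points (8, 16, 28, 56, 90, 150, 180). Two are unconditional, three (28, 56, 90) are lost under A, and two have the second route. Even with that route, the gap between tests is 150 − 16 = 134 nominal days. Under C the successive gaps are 28 − 16 = 12, 56 − 28 = 28, 90 − 56 = 34, 150 − 90 = 60 and 180 − 150 = 30 days. The date of clearance after a Day 16 positive is thus bracketed within at most 60 days under C, against 134 days at best under A.

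**A case the footnote does not cause.** If semen first turns positive after Day 16 with blood and urine negative, Days 28, 56 and 90 go untested under all three readings. That follows from conditional testing itself, not from naming Day 21.

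**The case against.** The strongest reply is that Appendix 4 already holds a workable rule. Note 2 does not name Day 21, and in the semen and vaginal rows the preceding entry is Day 16. Read that way, follow-up is complete. Specimens from Days 28, 56 and 90 are collected regardless and are stored under Section 9.3, so they can be assayed later. Days 150 and 180 have their own second route. Any genital detection on Day 8 or 16 already goes to the DSMB and FDA under Section 8.5.1.2. No vaccine virus was recovered from any fluid in the 20 recipients of 10^3 PFU (Section 2.3.2). Section 2.1 cites newer wild-type data with infectious virus in only 4% of PCR-positive semen samples, all within 30 days of symptom onset. The study is descriptive (Section 10.2), and shedding duration is a secondary objective.

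Much of this stands. A reader might infer that genital shedding cannot be followed after Day 16, or that the duration objective cannot be answered. The documents support neither, for the reasons just given.

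It does not remove the defect. The body text names Day 21 explicitly, and Day 21 is also the column before Day 28 in Appendix 4, so note 2 is at best ambiguous. Storage permits testing but does not instruct it. Cohort 2 receives ten times the dose of the recipients with no recovery. The objective covers RT-PCR as well as culture, and Section 2.1 reports wild-type RNA in semen for 2 to 6 months. Those wild-type figures do not predict the vaccine's behaviour, but they show why the later samples are collected.

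**Conclusion.** The Day 28 footnote is wrong as written for semen and vaginal secretions and must be reconciled with Appendix 4. Taken literally, it can leave all three intermediate genital time points (Days 28, 56 and 90) untested in a subject positive on Day 16. Clearance would then be bracketed no more tightly than 134 days, and only if untested specimens count as missing results. On the any-fluid reading the same loss occurs whenever blood and urine are negative on Day 21.

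The shedding-duration objective is put at risk, not made unanswerable: one reading of Appendix 4 avoids the problem, and the specimens survive. The conclusion assumes that staff follow Section 7.4.1 where it is more specific than the appendix. It matters only if a genital positive occurs, which had not happened at 10^3 PFU. The blank Day 21 cells in Appendix 4 come from a table read by program, but they agree with the Day 21 list in Section 7.4.1.

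**What to change.** In the Day 28 footnote of Section 7.4.1 and in Appendix 4 note 2, define the trigger separately for each fluid as the most recent earlier scheduled sample of that same fluid: Day 16 for semen and vaginal secretions, Day 21 for blood and urine. The existing Day 56 and Day 90 footnotes then work unchanged.

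In the same two places, state that recovery by culture or by RT-PCR meets the condition. The plan uses the word both ways: Section 2.3.2 speaks of recovery assessed by culture and PCR, while the infection definition in Section 3.2 is limited to infectious virus.

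The cost is two footnotes and assays on at most three specimens (Days 28, 56 and 90) per subject positive on Day 16, all from samples the schedule already collects. A subject still positive on Day 90 moves to the Day 150 and 180 collections that the plan already provides for. No visit is added.
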